F. Sample Size Estimation and Accrual

The endpoint of this pilot trial will be an immunological endpoint, i.e., the immune response rate at 6 months. Based on published results from a randomized trial using sipuleucel-T only in this population, in which proliferative T-cell responses specific for PAP were detected in 15 of 55 (27.3%) patients after immunization [7], and results from a phase I trial with this DNA vaccine only in which PAP-specific cytolytic T-cell responses were amplified after immunization in 7 out of 12 (58%) evaluable patients [23], it is anticipated that the immune response rate in the sipuleucel-T alone arm (Arm 1) will be 25% and that the addition of the pTVG-HP vaccine (Arm 2) will boost the response rate to at least 75%. An increase of 50% in the immune response rate will be considered as a clinically important difference. The following table shows the required sample sizes (per arm) to detect various differences in the immune response rates between the two arms with 80% power at the one-sided 5% significance level. These calculations are based on the stratified Mantel-Haenszel test with exact p-values.

Table 12.1 *Required sample sizes (per arm) to detect various differences in the immune response rates between the two arms with 80% power at the two-sided 5% significance level*

Immune Response Rate Arm 1 (sipuleucel-T alone arm)	Immune Response Rate: Arm 2 (sipuleucel-T + pTVG-HP vaccine arm)			
	70%	75%	80%	85%
15%	12	10	9	9
20%	15	12	10	9
25%	18	14	12	10
30%	23	18	15	12

A sample size of 14 patients per arm is proposed for this trial. This sample size is sufficient to detect an anticipated difference in the immune response rate of at least 50% (i.e., $\geq 75\%$ in Arm 2 vs. 25% in Arm 1) with adequate power ($\geq 80\%$) at the one-sided 5% significance level. The following table shows the attainable power levels to detect various differences in the immune response rates between arms at the one-sided 5% significance level, assuming a sample size of 28 evaluable (for immune response) patients.

Table 12.2: *Attainable power levels to detect various differences in the immune response rates between the two arms at the one-sided 5% significance level, assuming a sample size of 14 evaluable patients per arm*

	Immune Response Rate: Arm 2 (sipuleucel-T + pTVG-HP vaccine arm)			
Immune Response Rate Arm 1 (sipuleucel-T alone arm)	70%	75%	80%	85%
15%	85%	91%	96%	98%
20%	76%	85%	91%	96%
25%	65%	80%	84%	91%
30%	53%	65%	76%	85%

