A difference in the immune response rate of 55% between the two arms will be detected with at least 84% power. Analogously, a difference in the efficacy response rate of only 40% between the two arms will be detected with 53% power at the one-sided 5% significance level. In order to account for unevaluable patients, 30 eligible patients (15 per arm) will be accrued and randomized. Based on past experience with this patient population treated at our institution, we anticipate that the proposed total number of 30 patients will be accrued within 18 months. Each patient will be followed for at least 12 months.

G. Statistical Analysis Plan

G.1. General

This section outlines the statistical analysis strategy and procedures for the study. If after the study has begun changes are made to primary and/or key secondary objectives, or the statistical methods related to those objectives, then the protocol will be amended.

Summary tabulations will be presented that will display the number of observations, mean, standard deviation, median, range, minimum, and maximum for continuous variables and the number and percent per category for ordinal and categorical data. All endpoints of this study will be presented graphically where possible using boxplots and histograms for continuous variables and (stacked) bar charts for categorical variables. Data analysis will be performed using SAS[®] (SAS Institute Inc., Cary, North Carolina) version 9.2 or greater.

There are many comparisons made between the two trial arms for multiple measurements, both clinical and laboratory. However, since this a pilot study, no adjustment will be made for

multiple comparisons. Except for the primary immunological endpoint, where the comparison between arms will be conducted at the one-sided 0.05 significance level, all other comparisons will be made using a two-sided test at a significance level of 0.05 without adjustment for multiplicity.

G.2. Baseline Comparability

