All measurements (variables) collected at baseline will be summarized and compared between study arms. These include demographic variables, lab parameters (CBC and platelets, creatinine, alk phos, SGOT, total bilirubin, amylase, LDH, serum testosterone and PSA and PAP) and medical history information. Comparisons between study arms of baseline variables on a continuous scale will be performed using a two-sample t-test and/or nonparametric Wilcoxon Rank Sum test. Comparisons between study arms of baseline variables on a categorical scale will be performed using Fisher's exact test.

G.3. Analysis of the Primary Immunological Endpoint: Immune Response Rate

Immune responses, obtained at 6 months, will be summarized in tabular format. Ninety-five percent confidence intervals for the proportions of patients with an immune response will be constructed for each study arm. The comparison of immune response rates between study arms will be performed using the Cochran-Mantel-Haenszel test, stratified by estimated survival (< 18 months, \geq 18 months) using the Halabi nomogram [50]. Due to the small sample size, exact p-values will be computed using Zelen's exact test for equal odds ratios for stratified 2 X 2 tables.

As a secondary analysis, "durable" immune responses will be determined by the presence of immune responses at one or more of the 3, 9, and 12 month time points evaluated after randomization. Immune responses determined at the 3, 9 and 12 month time points will be summarized in tabular format and compared between study arms using the Cochran-Mantel-Haenszel test, stratified by estimated survival (< 18 months, \geq 18 months) using the Halabi nomogram [50]. Furthermore, a generalized linear mixed effects model for binomial data with a logit link function will be employed to evaluate the longitudinal effects of immune responses measured at the 3-month intervals.

G.4. Analysis of Secondary and Exploratory Clinical and Immunological Endpoints

G.4.1. Analysis of 12-month Progression-Free Survival Rate

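### The exact p-value for the primary endpoint is assigned to a test of whether the two strata agree, not of whether the two arms differ

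*Combined protocol and SAP*

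**What the plan says.** Section 12.G.3 gives two consecutive instructions for the primary endpoint, the immune response rate at 6 months. First: "The comparison of immune response rates between study arms will be performed using the Cochran-Mantel-Haenszel test", stratified by Halabi-predicted survival below or at least 18 months. Then, because the sample is small, "exact p-values will be computed using Zelen's exact test for equal odds ratios for stratified 2 X 2 tables".

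Two other sections bear on it. Section 12.F says of the sample-size tables: "These calculations are based on the stratified Mantel-Haenszel test with exact p-values". Section 12.G.1 singles out the primary endpoint as the one "where the comparison between arms will be conducted at the one-sided 0.05 significance level". The design assumptions in Section 12.F are response rates of 25% in Arm 1 and at least 75% in Arm 2, with 14 evaluable patients per arm.

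**The concern.** A test for equal odds ratios asks whether the treatment effect is the same size in the two strata. The primary objective asks whether there is a treatment effect at all, so the null hypothesis needed is a common odds ratio of 1. These are different hypotheses. Zelen's test fixes the total number of Arm 2 responders and looks only at how they divide between the strata. It therefore has no direction in favour of either arm, while the plan requires a one-sided comparison between arms.

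Followed literally, the p-value reported for the primary endpoint would almost never be small when the vaccine works equally well in both strata. A small value would mean that the strata disagree, and the power in Table 12.2 would not apply to it. If the error is noticed only at analysis, the exact method for the primary endpoint of an open-label trial would be chosen after the data are known.

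**Working it through.** **Inputs from the documents.** 14 evaluable patients per arm; 25% versus 75%; one-sided 0.05 (Sections 12.F and 12.G.1); two strata (Section 12.E).

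**Assumption.** The documents do not give stratum sizes. I took 7+7 and 4+10 per arm; 5+9 and 3+11 were also tried. Response rates are the same in both strata unless stated.

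**1. The plan's own figures.** The one-sided Fisher exact test, by full enumeration, reproduces 15 of the 16 sample sizes in Table 12.1 exactly and 15 of the 16 powers in Table 12.2 to within one point. For example, 15% vs 70% gives 85.1% (stated 85%) and 30% vs 70% gives 53.0% (stated 53%). The trial was therefore sized for a test of the arm difference. The exception is the design cell, 25% vs 75%: power at 14 per arm is 75.2% against the stated 80%, and 80% is first reached at 15 per arm. That is a separate point.

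**2. The two tests.** In stratum k, with n_k patients per arm and m_k responders in both arms together, the number of Arm 2 responders b_k given the margins has probability

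P(b_k) = C(n_k, b_k) · C(n_k, m_k − b_k) / C(2n_k, m_k).

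- Exact Mantel-Haenszel, one-sided: p = P(b_1 + b_2 ≥ observed total).
- Zelen: hold b_1 + b_2 at its observed value T, and sum the conditional probabilities of all splits (b_1, T − b_1) that are no more likely than the observed one.

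**3. Worked example: 2/7 in Arm 1 vs 5/7 in Arm 2, in both strata.** Here m_k = 7 and C(14,7) = 3,432.

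- Mantel-Haenszel: the weights of all pairs with b_1 + b_2 ≥ 10 sum to 366,031, so p = 366,031 / 3,432² = 366,031 / 11,778,624 = 0.031.
- Zelen: T = 10. The possible splits and their weights are (3,7) 1,225; (4,6) 60,025; (5,5) 194,481; (6,4) 60,025; (7,3) 1,225; total 316,981. The observed split (5,5) is the most likely, so every split counts and p = 316,981 / 316,981 = 1.00.

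**4. Extreme example: 0/7 vs 7/7 in both strata.** Mantel-Haenszel p = (1/3,432)² = 0.00000008. For Zelen, T = 14 allows only the split (7,7), so p = 1.00. The same happens whenever every Arm 2 patient responds, whatever Arm 1 does.

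**5. Rejection probabilities.** All tables were enumerated and weighted by the binomial probabilities.

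| True rates, Arm 1 vs Arm 2 | Per-arm strata | Exact Mantel-Haenszel, one-sided p ≤ 0.05 | Zelen p ≤ 0.05 |
|---|---|---|---|
| 25% vs 75% | 7+7 | 75.4% | 0.73% |
| 25% vs 75% | 4+10 | 75.6% | 0.89% |
| 25% vs 25% (no effect) | 7+7 | 1.9% | 0.73% |
| 10% vs 90% in one stratum, 90% vs 10% in the other | 7+7 | below 0.1% | 99.6% |

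Rows 1 and 3 show that, with 7+7 strata, Zelen's test rejects as often for an inert vaccine as for one with the planned effect. Row 4 shows what it does detect: disagreement between the strata.

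**6. How close to 1.** At 25% vs 75% the median Zelen p is 1.0 and p ≥ 0.99 occurs in 66% to 76% of trials over the four splits, but p falls below 0.5 in 24% to 32%.

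**The case against.** The sentence just before the disputed one names the Cochran-Mantel-Haenszel test for the arm comparison, which is the right type of test. Section 12.F refers to exact Mantel-Haenszel p-values, and Section 12.G.1 calls for a one-sided comparison between arms. Everything around the sentence points to an exact Mantel-Haenszel test, so this is most likely a misnamed procedure, and an analyst might notice that output labelled as a test of equal odds ratios does not answer the question. It is also fair to say that a p-value near 1 is the typical result at the planned rates and not a certain one, and that the stratum sizes are assumed.

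The reading of intent stands, and the consequence does depend on the text being followed. The instruction itself is not cured. Section 12.G.3 calls for exact p-values because the sample is small, so the large-sample Mantel-Haenszel p-value is not a fallback, and it names only one exact procedure. No other section corrects it. The rejection probability of Zelen's test stays below 1% over all four assumed splits at 14 per arm, so the conclusion does not hang on the stratum sizes. Pilot status is used in Section 12.G.1 only to waive multiplicity adjustment; the trial still declares a primary test with a significance level and a power.

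**Conclusion.** The concern holds. As written, the exact p-value for the primary endpoint tests homogeneity of the odds ratio across the survival strata and not the effect of adding pTVG-HP. Under the planned effect, equal in both strata, it would be significant in under 1% of trials, compared with about 75% for the exact stratified test of the arms. It conflicts with the one-sided comparison in Section 12.G.1 and with the test used for the sample size in Section 12.F. The figures assume 14 evaluable patients per arm, the same response rates in both strata, and the stratum sizes listed. This must be corrected before the primary analysis.

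**What to change.** Replace the sentence on Zelen's test in Section 12.G.3 with: *The one-sided exact p-value will come from the exact conditional Cochran-Mantel-Haenszel test that the common odds ratio equals 1, stratified by estimated survival (< 18 vs ≥ 18 months), and will be reported with the exact confidence interval for the common odds ratio.* The p-value clause resolves the contradiction; the interval is a useful addition. Zelen's test may stay as a descriptive check of homogeneity, labelled as such.

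The cost is one sentence, with no effect on patients, visits or data. If the study has begun, Section 12.G.1 requires a protocol amendment for a change to the primary method, and it should be made before the 6-month immune results are compared between arms.

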CD8+ T-cells, the presumed population mediating tumor cell destruction, and anti-tumor responses [17-20]. PAP is the target antigen of the autologous antigen-presenting cell sipuleucel-T vaccine, in which autologous peripheral blood mononuclear cells are loaded *ex vivo* with a PAP-GM-CSF fusion protein. A separate phase I clinical trial evaluated dendritic cells loaded with a murine homologue of PAP, and demonstrated immunogenicity of this approach [21]. In rodent studies, we have similarly demonstrated that PAP can be immunologically targeted using genetic vaccines, and a plasmid DNA vaccine in particular [18, 19]. We have previously reported the results of a phase I/II trial conducted in patients with early, PSA-recurrent (clinical stage D0) prostate cancer using this same DNA vaccine (pTVG-HP). No significant adverse events were observed in 22 subjects treated over a 12-week period of time. Moreover, several patients developed evidence of PAP-specific CD4+ and CD8+ T-cells, and several patients experienced a prolongation in the PSA doubling time, demonstrating immunological efficacy and suggesting a possible anti-tumor effect [22]. The presence of long-term IFN γ -secreting immune responses to PAP, detectable at multiple times months after immunization, were associated with increases in PSA doubling time, suggesting this might serve as a rational biomarker for efficacy [23]. Moreover, it was found that immune responses could be augmented months later with repeated immunizations, suggesting that DNA vaccines might provide a simple means of boosting immune responses from other priming immunizations [23]. These findings have justified further evaluation of this vaccine in a randomized phase II clinical trial, a study currently underway, and also specifically suggest that the pTVG-HP might be used in combination with sipuleucel-T to augment PAP-specific T-cell responses primed by that immunization strategy, as both vaccine approaches target the same antigen. This serves as the primary rationale for the current trial.

2. Background and Rationale

A. PAP is a tumor antigen in prostate cancer and PAP-specific CD8+ CTL can lyse prostate cancer cells

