The primary endpoint of the trial will be an immunological endpoint – the detection of augmented numbers of PAP-specific effector (IFN γ -secreting and/or granzyme B-secreting) and memory (proliferating) T-cell immune response after immunization, using blood obtained at 6 months for the primary analysis compared with pre-treatment. Immune response will be determined as a static time point at 6 months, and “durable” immune responses will also be determined by evaluation at 3, 9, and 12 months after study entry.

All subjects will undergo radiographic imaging (CT of abdomen and pelvis and bone scan) prior to treatment, and at 3-month intervals (or as clinically indicated). Radiographic disease progression will be defined using both RECIST 1.1 and PCWG2 published criteria [49], as detailed in Section 7. Based on the prior trials leading to the approval of sipuleucel-T, and because immune therapies are expected to require up to several months before radiographic responses or stabilization might be observed, the radiographic studies obtained at 3 months will not be used to define progression, rather will be used as the baseline for future comparison. That is, while baseline studies will be obtained prior to study registration, and radiographic progression may be expected in 50% of patients at 3 months, this will not be used to define progression necessitating patients come off study, rather disease progression occurring after this initial 3-month period. Time to progression will be determined from registration for all subjects. 1-year progression-free survival will be calculated for each treatment arm, as well as the median progression-free survival.

PSA doubling times will be calculated from all available values obtained within 3-6 months from the same clinical laboratory (when feasible) prior to study enrollment, up to and including the baseline value, and used to determine a pre-treatment PSA doubling time. Similarly, a post-treatment doubling time will be calculated from all PSA values obtained beginning with the PSA value at day 1 and continuing until the end-of study (or 1-year) value.

7. Measurement of Effect

A. Malignant Disease Evaluation

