 - Stage of prostate cancer, treatments for prostate cancer, and recent serum PSA level
 - New cancer diagnoses
 - New autoimmune disorders
 - New hematologic or neurologic disorders
 - Other new medical diagnoses
 - Date of death if patient deceased

10. **Response Monitoring**

A. **Immunological Monitoring**

Blood will be collected by either peripheral blood draw (up to 150 mL) or leukapheresis (50-100 mL) pre-immunization, after the initial three sipuleucel-T treatments, and at quarterly intervals up to one year, for immunological monitoring. From the heparinized blood, peripheral blood mononuclear cells (PBMC) will be prepared by density centrifugation over Ficoll-Paque using standard techniques. PBMC will be used directly for analysis, and residual material cryopreserved in liquid nitrogen using 90% autologous serum collected at the time of blood draw, or 90% fetal calf serum, and 10% DMSO. Sera will be prepared from the red-top tubes and stored in aliquots at -80°C for antibody analyses. $\text{IFN}\gamma$ and granzyme B ELISPOT analysis, PAP-specific T-cell proliferation, flow cytometric assays of antigen-specific cytokine secretion, and ELISA tests for antigen-specific antibodies, will be the primary methods of analysis. The primary antigens tested will be PAP (experimental), PSA (negative control), and tetanus toxoid (positive control). The primary immune analysis will be conducted at the 6-month time point, and compared with the pre-treatment time point, and for patients to be evaluable for immune response (primary endpoint), blood (PBMC and serum) from this time point must be available for analysis. However, immune monitoring will be conducted at the other time points indicated in secondary analyses to evaluate kinetic measures of immunity, and evaluate whether durable immune responses of particular phenotypes are elicited and/or maintained. Assays may be conducted at the time of sample collection (fresh) and/or batched and performed at one time from multiple cryopreserved samples collected at different time points. Other methods of effector and regulatory T-cell response to PAP and other human tissue antigens may be used. Some assays may assess immune responses to the PA2024 (PAP-GM-CSF) fusion antigen or to GM-CSF.

A.1. **Quantitative assessment of PAP-specific CD8+ T-cell effector immunity**

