An immune response will be defined based on the detection of augmented numbers of PAP-specific effector (IFN γ -secreting and/or granzyme B-secreting) and/or memory (proliferating) T-cell immune response after immunization, using blood obtained at 6 months for the primary analysis compared with pre-treatment. Specifically, a positive antigen-specific response resulting from immunization will be defined as a PAP-specific response by two or more of these three tests detectable at the 6-month post-treatment time point that is significantly ($p < 0.05$, two-sided using a two-sample t-test) higher than to media only, at least 3-fold higher than the mean baseline value, and with a frequency > 10 per 10^6 PBMC, based on 8-well replicate assays (for ELISPOT-based assays) or triplicate assays (for proliferation analysis). Otherwise, a patient will be declared as an immune non-responder.

Immune response will be determined as a static time point at 6 months, and “durable” immune responses will also be determined by the presence of a PAP-specific immune response by the criteria above detectable at 3, 9, or 12 months after study entry.

C.2. Secondary Clinical and Immunological Endpoints

C.2.1. Time to Progression

Time to progression will be defined as a function of baseline time points in two ways:

- (1) *Time to progression from randomization*: Time elapsed from randomization until disease progression or death. If a patient doesn't experience a disease progression or death event before the end of the follow-up period, then the observation for this patient will be censored.
- (2) *Time to progression from 3 months post-randomization*: Time elapsed from the 3 months disease progression assessment until disease progression or death. If a patient doesn't experience a disease progression or death event before the end of the follow-up period, then the observation for this patient will be censored.

The rationale for defining time to progression as a function of baseline time points (date of randomization and 3-month disease assessment) is described in Section 6 (B).

C.2.2. Twelve-month Progression Free Survival Rate

The 12-month progression free survival rate will be defined as the proportion of patients progression free at the 12 month (post-randomization) disease assessment time point.

C.2.3. Overall Survival

Overall survival will be defined as the time interval from randomization to death from any cause or to the last follow-up in censored patients.

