The number of circulating tumor cells per million PBMC will be summarized in terms of medians and ranges, stratified by study arm and assessment time point. The nonparametric Wilcoxon Signed Rank test will be used to evaluate the effects of treatment on the number of circulating tumor cells within each study arm. The comparison of changes in the number of circulating tumor cells between study arms will be performed using the nonparametric, stratified, Wilcoxon Rank Sum test. Results will be presented graphically over time, and trends (increase, decrease, stable) will be assessed over time.

G.5.2. Analysis for evaluating PAP-specific antibody and T-cell immune responses following treatment with sipuleucel-T and DNA vaccine

PAP-specific antibody and T-cell immune responses, evaluated by multiple different measures described in Section 10.A, following treatment with sipuleucel-T and DNA vaccine will be summarized in tabular format.

G.5.3. Analysis for evaluating whether PAP-specific immune response is associated with prolonged (1 year) progression-free survival

Logistic regression analysis will be conducted to evaluate whether PAP-specific immune response is associated with prolonged (1-year) progression-free survival. The dependent variables will be 12-month progression free survival while treatment arm and PAP-specific immune responses (no vs. yes) will be included as covariates. The results will be reported in terms of odds ratios and the corresponding 95% confidence intervals.

G.5.4. Analysis for evaluating whether baseline immune responses (Th1 type or regulatory type) predict for immune responses elicited/augmented following treatment with sipuleucel-T +/- DNA vaccine

Logistic regression analysis will be conducted to evaluate whether baseline immune responses (Th1-type or regulatory type) predict for immune responses elicited/augmented following treatment with sipuleucel-T +/- DNA vaccine. 6-month and durable immune response at 3,6 or 12 months will be included as dependent variables in this analysis while treatment arm and baseline PAP-specific immune responses (no vs. yes) will be included as covariates. Odds ratios and the corresponding 95% confidence intervals will be reported.

G.5.5. Analysis for evaluating whether treatment elicits immunologic antigen spread to other prostate associated antigens

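### The durable-response rule in G.3 and C.1 is met by one positive visit, and G.5.4 uses a different visit list, so single-visit responses can be labelled durable

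*Combined protocol and SAP*

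**What the plan says.** Durable response is described in four places.

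- **Section 6.B (Endpoints):** durable "immune responses will also be determined by evaluation at 3, 9, and 12 months after study entry". The number of positive visits needed is not given.
- **Section 12.C.1:** a PAP-specific response "by the criteria above detectable at 3, 9, or 12 months after study entry". One visit is enough.
- **Section 12.G.3:** "determined by the presence of immune responses at one or more of the 3, 9, and 12 month time points evaluated after randomization". One visit is enough, and this is stated outright.
- **Section 12.G.5.4:** "6-month and durable immune response at 3,6 or 12 months will be included as dependent variables in this analysis". Month 9 is gone and month 6 has come in, although 6-month response is already a separate outcome in the same sentence.

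Section 10.A gives the purpose of the visits other than month 6: to "evaluate whether durable immune responses of particular phenotypes are elicited and/or maintained". G.3 also plans tables and between-arm tests for months 3, 9 and 12, and a binomial mixed model over the 3-monthly visits.

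**The concern.** A durability rule should separate responses that last from those that do not. The G.3 and C.1 rule asks only whether a patient was positive at least once among three visits. A patient positive at month 3 and negative at months 6, 9 and 12 is classed as durable. A patient positive at month 6 alone is not durable under G.3 but is durable under G.5.4.

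The direction is also wrong. A rate of response at any of several visits cannot be lower than the rate at one of them, whereas a rate of response that persists from a given visit cannot be higher than the rate at that visit.

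Month 3 needs particular care in Arm 2. Day 85 falls 14 days after DNA immunization #3 (day 71), so a short-lived response to that dose could earn the label. This does not apply to Arm 1, whose last infusion was on day 32.

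At stake are the reported durable rate, its comparison between arms, and the G.5.4 regression, which would model a differently defined variable under the same name.

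**Working it through.** The plan gives no rate, power or sample size for durable response, so there is no figure to reproduce. The check has two parts.

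**1. What each definition does with single-visit patterns**

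| Positive only at | G.3 / C.1 | G.5.4 |
|---|---|---|
| Month 3 | durable | durable |
| Month 6 | not durable | durable |
| Month 9 | durable | not durable |
| Month 12 | durable | durable |

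Section 6.B cannot be placed in the table because it gives no count.

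Timing from the Study Calendar: 85 − 71 = 14 days from the previous DNA dose to month 3 (Arm 2); 85 − 32 = 53 days from the last infusion (Arm 1). In Arm 2, months 6, 9 and 12 (weeks 24, 36, 48) each fall 12 weeks after the previous scheduled DNA dose.

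**2. How much this could matter (illustration)**

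Inputs: response rates of 25% (Arm 1) and 75% (Arm 2) and 14 evaluable patients per arm, from Section 12.F. The rates are month-6 planning rates; using them at every visit is an assumption. The within-patient correlation ρ is not in the documents and is varied.

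*Independent visits (ρ = 0):*

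- Durable under G.3 = 1 − (1 − p)³. Arm 1: 1 − 0.75³ = 0.578. Arm 2: 1 − 0.25³ = 0.984.
- Labelled durable but positive at only one of the four visits = 3p(1 − p)³. Arm 1: 3 × 0.25 × 0.75³ = 0.316. Arm 2: 3 × 0.75 × 0.25³ = 0.035.
- Share of those labelled durable: 0.316 / 0.578 = 55% (Arm 1); 0.035 / 0.984 = 4% (Arm 2).

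*Correlated visits:* a latent normal model with equal correlation ρ between visits. Given a patient effect z ~ N(0, 1), the visit probability is q(z) = Φ[(Φ⁻¹(p) + √ρ·z) / √(1 − ρ)]. Each formula is averaged over z with q in place of p.

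| Quantity at ρ = 0.5 | Formula | Arm 1 | Arm 2 |
|---|---|---|---|
| Durable under G.3 | E[1 − (1 − q)³] | 46% | 93% |
| Positive at one of four visits, as share of durable | E[3q(1 − q)³] / row 1 | 38% | 7% |
| Positive at month 3 alone, of all patients | E[q(1 − q)³] | 6% | 2% |
| Classified differently by G.3 and G.5.4, of all patients | E[2q(1 − q)³] | 12% | 5% |
| Month 6 and again at month 9 or 12 | E[q(1 − (1 − q)²)] | 17% | 70% |

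In Arm 1 the G.3 rate runs from 58% at ρ = 0 through 51%, 46% and 41% (ρ = 0.3, 0.5, 0.7) to 34% at ρ = 0.9. The single-visit share falls from 55% to 19% over the same range.

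In patients, at ρ = 0.5 the single-visit durable group is 3 × 0.059 × 14 ≈ 2.5 in Arm 1 and 3 × 0.023 × 14 ≈ 1 in Arm 2.

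A beta-binomial model with intraclass correlation 0.5 gives 40% and 88% for the G.3 rule, against 25% and 75% at a single visit. The two correlation scales are not the same, but the direction agrees.

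**The case against.** **The word 'also' may make month 6 the anchor.** Sections 6.B and C.1 fix month 6 as the static response and then say that durable responses will also be determined at the other visits. Leaving month 6 off that list makes sense if a month-6 response is presupposed. Under that reading the rule is month 6 plus any other visit, about 19% in Arm 1 at ρ = 0.5. But no text states the condition, and G.3 sets an explicit rule without it.

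**Transience stays visible.** The visit tables and the mixed model in G.3 would show it. This stands, but they do not change who is labelled durable or what G.5.4 models.

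**G.5.4 is probably a slip for 3, 9 or 12.** Quite likely, since month 6 is already a separate outcome there. It still has to be corrected before analysis.

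**The stakes are modest.** This is a secondary analysis in a pilot without multiplicity adjustment. That stands.

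A reader might also infer more than the documents support:

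- *That most durable responders would be transient.* Counting only months 3, 9 and 12, 54% of Arm 1 patients labelled durable at ρ = 0.5 have one positive visit. That ignores month 6: a patient positive at months 6 and 9 is not transient. With month 6 counted the share is 38%, and 7% in Arm 2.
- *That extra visits inflate the rate by chance.* The 25% is an anticipated true response rate, not an error rate, and C.1 demands two of three assays, each with a significance test, a 3-fold rise and a frequency threshold.
- *That the Introduction's description of responses "detectable at multiple times months after immunization" defines this endpoint.* It reports an earlier trial in PSA-recurrent disease. The mismatch that counts is with Section 10.A.

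**Conclusion.** The concern holds as a defect of definition. Followed exactly, G.3 and C.1 label a response at one visit durable, and G.5.4 applies the same name to a different visit set in which the primary response alone qualifies. This follows from the text and needs no assumption.

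The size is illustrative. It rests on the month-6 planning rates holding at every visit and on an assumed equal correlation between visits. At ρ = 0.5, single-visit responders are about 38% of Arm 1 and 7% of Arm 2 patients labelled durable, with an Arm 1 range of 19% to 55% for ρ from 0.9 to 0. The extreme case, positive at month 3 and never again, is uncommon: about 6% and 2% of patients.

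The month-6 primary comparison is untouched. The change should be made because the label and the G.5.4 outcome would otherwise not mean what Section 10.A intends.

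**What to change.** 1. Write one definition and use it in 6.B, C.1, G.3 and G.5.4. It should require a response at two or more visits. Month 6 and again at month 9 or 12 is one example; other persistence rules, such as any two visits, are defensible, and the choice should be fixed before the data are seen.
2. Correct the visit list in G.5.4, so that a month-6 response cannot count as durable by itself.
3. State how missing visits are handled, including for patients who come off study early but continue immune blood draws.
4. Report the any-visit rate as response at any time, and keep the single-visit tables.

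The cost is wording only, with no new samples or visits. The reported durable rate will be lower: in the illustration at ρ = 0.5, the month 6 plus 9 or 12 rule gives 17% and 70% in place of 46% and 93%. Patients missing late visits may be unclassifiable, which matters with 14 evaluable patients per arm.
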